3.2 Primary Study Endpoints

For Phase Ib, the primary endpoint is identification of toxicities, tolerability and definition of a recommended phase II dose (RP2D) of Q3WK infusions of CDX-3379 in combination with once daily oral administration of trametinib.

For Phase II, the primary endpoint is an estimation of the overall response rate and duration of response in patients treated with CDX-3379 in combination with trametinib in *NRAS* mutant and WT melanoma.

3.3 Secondary Study Endpoints

For Phase 1b, the secondary endpoints are to assess clinical activity and steady-state pharmacokinetics of CDX-3379 and trametinib

For Phase II, the secondary endpoints are description of antitumor activity of the combination CDX-3379 and trametinib and include progression free survival (PFS) and overall survival (OS).

3.4 Exploratory Endpoints

Exploratory endpoints for both phase Ib and II include evaluation of pharmacodynamic markers of CDX-3379 and trametinib activity in serial tumor biopsies and potential predictive biomarkers of response and resistance to CDX-3379 and trametinib. Evaluations may include, but are not limited to, ERBB3, pERBB3, FOXD3, ERBB2, pERBB2, EGFR, pAKT, PTEN, ERK1/1, pERK1/2, DUSP4, NRG1 (neuregulin), NRG2, transforming growth factor alpha (TGF α) and amphiregulin (AREG), as well as other markers identified to be integral to ERBB3 and MEK inhibition.

3.5 Primary Safety Endpoints

Safety assessments will consist of monitoring and recording all adverse events, including serious adverse events as well as blood monitoring of hematologic and chemistry values with each cycle of therapy. Patients will also be clinically assessed with regular monitoring of vital signs and physical exam. The secondary endpoints of the phase Ib portion of the study includes adverse event rates. Refer to Section 8 for further information on safety monitoring.

Determination of final MTD/RP2D will be guided by the incidence of drug-related side effects and dose de-escalations occurring within 6 weeks (two cycles) which allows for substantial amount of time for unexpected toxicities with combination of CDX-3379 with trametinib. This is detailed in section 3.1.

CONFIDENTIAL

4 Subject Enrollment and Withdrawal

4.1 Inclusion Criteria

1. Read, understood, and provided written informed consent and, if applicable, Health Insurance Portability and Accountability Act (HIPAA) authorization after the nature of the study has been fully explained and must be willing to comply with all study requirements and procedures.
2. Male or female patients who are 18 years of age or older.
3. Patients with a diagnosis of histologically confirmed advanced (defined as unresectable stage III or IV) melanoma with the *NRAS* Q61 mutation or *BRAF/NRAS* WT who are refractory to or intolerant of existing therap(ies) known to provide clinical benefit for their condition, including anti PD-1 and/or CTLA-4 agent.
 - Any CLIA certified mutation testing is acceptable to document mutation status.
4. Patients must have adequate cardiac function as demonstrated by a left ventricular ejection fraction (LVEF) $\geq 50\%$ as determined by a multigated acquisition (MUGA) scan or echocardiogram.
5. Patients must have archival tissue and at least one disease site amenable to biopsy:
 - For phase Ib, all patients will undergo fresh tumor biopsy
 - For phase II, five patients with *NRAS* mutation and five patients with *BRAF/NRAS* WT melanoma will undergo fresh tumor biopsy
6. Measurable (target) disease by Response Evaluation Criteria In Solid Tumors (RECIST 1.1) criteria. Target lesions selected for tumor measurements should be those where additional (eg palliative) treatments are not indicated or anticipated.
 - Measurable disease per RECIST 1.1 requirements: defined as longest diameter to be recorded for non-nodal lesions $> 10\text{mm}$ and short axis for nodal lesions $> 15\text{ mm}$ using conventional techniques
7. All residual toxicity related to prior radiotherapy or anticancer therapies (excluding alopecia, grade 2 fatigue, vitiligo or endocrinopathies on stable replacement therapy) must resolve to grade 1 severity or less (or returned to baseline) prior to receipt of study treatment.
8. Adequate electrolytes, liver, renal, and hematology function as defined below:
 - a. Hemoglobin $\geq 9\text{ g/dL}$
 - b. Absolute neutrophil count $\geq 1500/\text{mm}^3$
 - c. Platelet count $\geq 100,000/\text{mm}^3$
 - d. Aspartate aminotransferase (AST) and alanine aminotransferase (ALT) $\leq 2.5 \times$ upper limit of normal (ULN) ($\leq 5 \times$ ULN for cases involving liver metastasis)
 - e. Bilirubin $\leq 1.5 \times$ ULN ($\leq 5 \times$ ULN for cases of documented or suspected Gilbert's disease)
 - f. Serum creatinine $\leq 1.5\text{ g/dL}$ or calculated creatinine clearance (CrCl) $\geq 60\text{ mL/min}$ for patients with serum creatinine $> 1.5 \times$ ULN
 - g. Serum magnesium, calcium and potassium within normal limits
9. Life expectancy ≥ 12 weeks
10. ECOG performance status (PS) ≤ 1
11. Willing and able to comply with scheduled visits, treatment plan, and laboratory tests.
12. Screening EKG without clinically significant abnormalities.
13. Corrected (Fridericia's) QTcF must be < 480 milliseconds.

CONFIDENTIAL

14. Allowance of prior therapy regimens:
 - No limit on prior number of regimens
 - Must have completed prior cytotoxic chemotherapy a minimum of 4 weeks prior to starting study treatment (except for bis-chlorethynitrosurea (BCNU)), which must have been completed a minimum of 6 weeks prior to starting therapy.
 - Prior localized radiation therapy must have been completed a minimum of 2 weeks prior to starting therapy and the patient must have baseline imaging with a full body PET-CT or CT scans of the chest, abdomen, and pelvis and within 4 weeks prior to study enrollment.
 - For CNS metastases, disease must be treated and demonstrate stability with Brain MRI a minimum of 4 weeks prior to starting therapy.
15. Both male and female patients enrolled in this trial must agree to use highly effective contraception during the course of the trial and for at least for 6 months after the final dose of CDX-3379 (an effective form of contraception is an oral contraceptive or a double barrier method), or greater, as in accordance with the label requirements for trametinib. Patients and/or partners who are surgically sterile or postmenopausal are exempt from this requirement.
 - Women of child-bearing potential, defined as all women physiologically capable of becoming pregnant, unless they are using highly effective methods of contraception during dosing and for 3 months after stopping study drug. Highly effective contraception methods include:
 - Total abstinence or
 - Male or female sterilization or
 - Combination of any two of the following (a+b or a+c or b+c):
 - (a) Use of oral, injected or implanted hormonal methods of contraception; hormonal contraceptives are not acceptable as a sole method of contraception.
 - (b) Placement of an intrauterine device (IUD) or intrauterine system (IUS)
 - (c) Barrier methods of contraception: condom or occlusive cap (diaphragm or cervical/vault caps) with spermicidal foam/gel/film/cream/vaginal suppository
16. Women are considered post-menopausal and not of child bearing potential if they have had 12 months of natural (spontaneous) amenorrhea with an appropriate clinical profile (e.g. age appropriate, history of vasomotor symptoms) or have had surgical bilateral oophorectomy (with or without hysterectomy) or tubal ligation at least six weeks ago. In the case of oophorectomy alone, only when the reproductive status of the woman has been confirmed by follow up hormone level assessment is she considered not of child bearing potential.

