12. Use of other investigational drugs within 2 weeks or 5 half-lives (whichever is longer) prior to study treatment administration.
13. A marked baseline prolongation of QT/QTc interval (e.g., repeated demonstration of a QTc interval >450 ms); additional risk factors for torsades de pointes (TdP) (e.g., a history of heart failure, family history of Long QT Syndrome, or active hypokalemia or uncorrectable electrolyte abnormality); significant cardiovascular disease including unstable angina pectoris, uncontrolled hypertension or arrhythmia, congestive heart failure (New York Heart Association Class III or IV) related to primary cardiac disease, uncontrolled ischemic or severe valvular heart disease; or any of the following within 6 months prior to the first dose of study treatment: myocardial infarction, severe/unstable angina, coronary artery bypass graft, congestive heart failure, cerebrovascular accident, transient ischemic attack.
14. Requirement for chronic immunosuppressive medication including systemic corticosteroids above the physiologic dose (defined as 20 mg/day prednisone or the equivalent).
15. Any other acute or chronic medical or psychiatric condition or laboratory abnormality that could increase the risk associated with trial participation or trial drug administration or could interfere with the interpretation of trial results and, in the judgment of the investigator, would make the patient inappropriate for entry into the trial.
16. Known alcohol or drug abuse.
17. Sexually active males must use a condom during intercourse while taking the drug and for 3 months after stopping study drug and should not father a child in this period. A condom is required to be used also by vasectomized men in order to prevent delivery of the drug via seminal fluid.
18. Inability to swallow pills
19. Patients unwilling or unable to comply with the protocol.

CONFIDENTIAL

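### Inclusion 15 and exclusion 17 give different post-treatment contraception periods (6 versus 3 months), and inclusion 15 names a pill that its own sub-bullet bars as the only method

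*Combined protocol and SAP*

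**What the plan says.** Three texts set the post-treatment period.

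- Inclusion 15, lead sentence, both sexes: contraception during the trial and "for at least for 6 months after the final dose of CDX-3379". A label clause allows a longer period and no shorter one.
- Inclusion 15, sub-bullet, women of child-bearing potential: highly effective "methods of contraception during dosing and for 3 months after stopping study drug".
- Exclusion 17, men: "Sexually active males must use a condom during intercourse while taking the drug and for 3 months after stopping study drug". Men should also not father a child in that period.

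Two texts set the method. The lead sentence of inclusion 15 says in parentheses that "an effective form of contraception is an oral contraceptive or a double barrier method". The sub-bullet lists abstinence, sterilization, or a pair of methods from different classes: (a) hormonal, (b) intrauterine, (c) barrier. Under (a) it adds that "hormonal contraceptives are not acceptable as a sole method of contraception".

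On sterility, inclusion 15 says: "Patients and/or partners who are surgically sterile or postmenopausal are exempt from this requirement". Exclusion 17 says: "A condom is required to be used also by vasectomized men", and gives as its reason that drug could be passed on in seminal fluid.

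**The concern.** These duties continue after treatment, so the eligibility check at registration does not settle how long they last. They depend on what the patient is told. A patient told 3 months could stop before the 6-month floor. A woman told what the parenthesis says could rely on a pill alone.

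Little else in the protocol would catch the error. As printed, the schedule in section 6.7 has urine pregnancy tests at screening and in the treatment cycles but none at the end-of-treatment visit, and the Novartis pregnancy reporting in section 8.4 covers pregnancies during study treatment. A second site is planned, so two sites could read the rule differently.

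**Working it through.** There is no planned figure to reproduce. The check compares the end dates of the rules and then the permitted methods.

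**Duration.** Set month 0 at the final CDX-3379 dose. Let g be the number of months from then to the stop date that starts the 3-month clock.

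- End of the 6-month floor: month 6.
- End of the 3-month rule: month g + 3.
- Shortfall of the 3-month rule against the floor: 6 - (g + 3) = 3 - g, or none if g is 3 or more.

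What g can be depends on what study drug means in these two criteria, which they do not say.

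| Reading of study drug | Possible g | Shortfall |
|---|---|---|
| CDX-3379 | g = 0 always | 3 months |
| Last of either drug | g of 0 or more | 3 at g = 0; 2 at g = 1; 1 at g = 2; none from g = 3 |
| Trametinib | any sign | as the row above if trametinib stops later; more than 3 if it stops first, e.g. 3 - (-1) = 4 at g = -1 |

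The g = 0 case is realistic. Section 5.2 ends treatment at progression, and section 1.6.2 holds both drugs together unless the side effect is specific to trametinib. The other cases are possible too. Section 1.6.1.1.1 stops CDX-3379 after a grade 3 or 4 infusion reaction without saying that trametinib stops. Table 1 in section 1.6.1.2.1 stops trametinib permanently for retinal vein occlusion or pneumonitis, which section 1.6.2 treats as specific to trametinib.

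The same formula shows that 6 months alone is not always the stricter rule. At g = 5 on the last-of-either reading, the 3-month rule runs to 5 + 3 = month 8. Stopping at month 6 would leave 6 - 5 = 1 month of cover after trametinib. A rule that meets both clocks ends at the larger of 6 and g + 3: month 6 at g = 0, 2 or 3, and month 8 at g = 5.

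**Method.** An oral contraceptive alone is (a) alone, which the sub-bullet expressly rejects. A double barrier is (c) with (c), and the listed pairs are a+b, a+c and b+c. It is therefore not on the list, but the protocol introduces the list with the word include, so its exclusion is implied rather than stated.

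**Exemption.** The exemption in inclusion 15 is from the contraception requirement. The condom rule for vasectomized men in exclusion 17 concerns drug exposure through seminal fluid. The purposes differ, so both can hold. What is missing is a sentence saying so.

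**The case against.** The strongest reply is that the texts can all be obeyed at once. Section 11.2 requires every criterion to be met, inclusion 15 sets a minimum, and sections 6.5 and 6.6 count the last dose from trametinib. On that view there are two clocks, 6 months from CDX-3379 and 3 months from trametinib, and a patient follows whichever ends later.

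That is a sensible reading, and it is the rule proposed below, but the protocol does not state it. Section 11.2 governs enrollment. Sections 6.5 and 6.6 fix the last dose for the progression biopsy and for survival follow-up, not for contraception. Neither criterion refers to the other's period.

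Several parts of the reply do stand, and they rule out stronger readings that a reader might infer:

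- The sterile exemption and the vasectomy rule might look contradictory. They are not, because the condom rule states its own purpose.
- It might seem that neither method named in the parenthesis is allowed. Only the pill-alone conflict is explicit.
- It might seem enough to write 6 months everywhere. That would delete the only explicit post-trametinib period and could shorten cover when trametinib continues more than 3 months after CDX-3379.
- A shortfall of 3 months is not a fixed figure. It depends on which drug starts the clock and on when each drug stops.

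**Conclusion.** The protocol states two different post-treatment contraception periods for the same patients, 6 months and 3 months, and does not say which governs. If both drugs stop together the difference is 3 months, for women and for men. Within inclusion 15, the oral contraceptive named in the lead sentence conflicts with the bar on hormonal methods alone. The double-barrier and vasectomy items need clarification only.

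A reader might go further and infer that patients are being under-protected. The documents do not show that: the consent form and the trametinib label decide what patients are told, and neither was available for review. This is a minor drafting fault in a patient-safety rule. It does not touch alpha, power or sample size.

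**What to change.** 1. Put one period in the lead sentence of inclusion 15, in its sub-bullet for women, and in the exclusion 17 rule on condoms and not fathering a child: *until the later of 6 months from the last CDX-3379 dose and 3 months from the last dose of either study drug, or longer if the trametinib label so requires.*
2. Delete the parenthesis on oral contraceptives and double barriers, and refer to the two-method list instead.
3. Add to the exemption in inclusion 15 that it does not remove the exclusion 17 condom rule, which is there for seminal-fluid exposure. Whether vasectomized men should use condoms for longer than the present 3 months is for the sponsor to decide, because the documents give no basis for either answer.

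The cost is a few sentences, a check of the consent form against them, and a somewhat longer stated period for some patients. It needs no new visit, procedure or patient.

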4.2 Exclusion Criteria

Patients will be excluded from the study for any of the following reasons:

1. Received CDX-3379 or other anti-ErbB3 targeted agents previously.
2. Received trametinib or other MEK inhibitor agents previously.
3. Any concurrent chemotherapy, radiotherapy, immunotherapy, biologic or hormonal therapy for cancer treatment. Concurrent use of hormones for non-cancer related conditions (e.g., insulin for diabetes and hormone replacement therapy) is acceptable.
4. Other prior malignancy active within 2 years, except for localized prostate cancer, cervical carcinoma in situ, non-melanomatous carcinoma of the skin, stage 1 differentiated thyroid cancer or ductal carcinoma in situ of the breast that has/have undergone curative surgery or radiation.

CONFIDENTIAL

5. Active central nervous system (CNS) metastases are excluded. Known brain metastases must have been previously treated and asymptomatic for 2 weeks and not progressive in size or number for 4 weeks prior to enrollment, documented via scans. Continued use of anticonvulsants (in the absence of any suspicion of progressive brain metastases) is acceptable. Patients must currently be on a stable, lowest possible dose of steroids.
6. Radiation therapy within 14 days prior to the first scheduled dose in this study, including, in addition (if necessary), the timeframe for resolution of any actual or anticipated toxicities from such radiation.
7. Known HIV, hepatitis B or hepatitis C infection, or active infection requiring systemic intravenous therapy.
8. History or current evidence of retinal vein occlusion (RVO) or current risk factors for RVO (e.g. uncontrolled glaucoma or ocular hypertension, history of hyper viscosity or hypercoagulability syndromes).
9. Use of any monoclonal based therapies within 4 weeks (excluding cetuximab which does not require a wash-out), and all other immunotherapy (tumor vaccine, cytokine, or growth factor given to control the cancer) within 2 weeks, prior to the first dose of study treatment.
10. Chemotherapy within 4 weeks (except for bis-chlorethynitrosurea (BCNU), which must have been completed a minimum of 6 weeks) prior to starting therapy.
11. Major surgery within 4 weeks prior to the first dose of study treatment. Surgery requiring local/epidural anesthesia must be completed at least 72 hours before study drug administration and patients should be recovered.
12. Use of other investigational drugs within 2 weeks or 5 half-lives (whichever is longer) prior to study treatment administration.
13. A marked baseline prolongation of QT/QTc interval (e.g., repeated demonstration of a QTc interval >450 ms); additional risk factors for torsades de pointes (TdP) (e.g., a history of heart failure, family history of Long QT Syndrome, or active hypokalemia or uncorrectable electrolyte abnormality); significant cardiovascular disease including unstable angina pectoris, uncontrolled hypertension or arrhythmia, congestive heart failure (New York Heart Association Class III or IV) related to primary cardiac disease, uncontrolled ischemic or severe valvular heart disease; or any of the following within 6 months prior to the first dose of study treatment: myocardial infarction, severe/unstable angina, coronary artery bypass graft, congestive heart failure, cerebrovascular accident, transient ischemic attack.
14. Requirement for chronic immunosuppressive medication including systemic corticosteroids above the physiologic dose (defined as 20 mg/day prednisone or the equivalent).
15. Any other acute or chronic medical or psychiatric condition or laboratory abnormality that could increase the risk associated with trial participation or trial drug administration or could interfere with the interpretation of trial results and, in the judgment of the investigator, would make the patient inappropriate for entry into the trial.
16. Known alcohol or drug abuse.
17. Sexually active males must use a condom during intercourse while taking the drug and for 3 months after stopping study drug and should not father a child in this period. A condom is required to be used also by vasectomized men in order to prevent delivery of the drug via seminal fluid.
18. Inability to swallow pills
19. Patients unwilling or unable to comply with the protocol.

CONFIDENTIAL

4.3 Inclusion of Women and Minorities

Both men and women of all races and ethnic groups are eligible for this trial.

4.4 Subject Recruitment and Screening

The inclusion and exclusion criteria in this study should not have a negative effect on the enrollment of the desired populations.

Eligible patients with advanced stage *NRAS* mutant and WT melanoma age 18 years and older who agree to participate in the study will be identified from the Laura and Isaac Perlmutter Cancer Center outpatient melanoma practice of the clinical investigators during a routine office visit or consult. Patients will also be recruited through NYU Langone Health and an additional site, the University of Pennsylvania, which will be added. All participants will be required to sign informed consent prior to trial enrollment. After signing informed consent, subjects will provide an archived tissue sample.

4.4.1 Method of Subject Identification and Recruitment

Target enrollment for this study is 44 patients. The target accrual goal at NYU is 10 patients per year.

The patients who are eligible for this research study come directly from the study investigators' clinical patient population. Thus, the investigators are very familiar with their patients' disease status and potential eligibility given the protocol's inclusion and exclusion criteria. The investigator will approach eligible potential subjects and explain the study in a private room, including the reasons why subjects will be eligible, risks, benefits, and the regimes to be evaluated. They will also receive the informed consent document to read. Consent will be obtained in a private room by the PI, Co-Investigator, or research coordinator/research nurse at the time of the subject's visit prior to any study assessments/procedures. The subjects will be given a chance to ask questions to the person consenting him/her and will be able to take the consent home to discuss it with family/friends prior to signing. If the subject agrees s/he will sign the consent form either at the first contact (if the investigator/delegate is convinced that the subject understands) or at the time of a return visit after having had time to study the consent in more depth. Study procedures will not begin until after the consent form has been properly obtained. The subject is entitled to decide not to participate in the trial, without affecting their right to other medical care, and may discontinue participation in the trial at any time without penalty or loss of benefits to which they are entitled.

The Principal Investigator will:

1. Obtain signed and dated informed consent from the potential subject before any study specific procedures are performed.
2. Determine patient eligibility; see Section 4.1 and 4.2
3. Submit registration to NYU Langone Health Perlmutter Cancer Center CTO
4. Receive registration confirmation from the NYU Langone Health Perlmutter Cancer Center CTO, including a unique study identification number assigned to the patient that will be distributed to the study team upon registration of the patient.

CONFIDENTIAL

The informed consent process and documentation follows that established procedures of the NYU Langone Health Perlmutter Cancer Center Clinical Trials Office.

